2. OBJECTIVES

To provide an overview of existing utilization patterns for warfarin and the NOAC medications as they become available in patients with non-valvular atrial fibrillation at risk for stroke. Specifically:

-
- Examine treatment initiation, switching and discontinuation.
-
- Update initial analyses on a 6-month basis.

3. STUDY DESIGN

This study will use a cohort design with descriptive analyses, using data from 2009-2015. It will be conducted within two US-based longitudinal healthcare claims databases (MarketScan and UnitedHealth Research Database, see also section 3.1 for more details). Cohort selection and all analyses will be conducted separately within each data source.

3.1 DATA SOURCES

The data source for this project is a combination of claims data from UnitedHealth, a commercial health insurer, and MarketScan, a research claims database from commercial employer-sponsored health plans both of which provide comprehensive medical coverage for members with active policies.

3.2 STUDY POPULATION

From the UnitedHealth Research Database and MarketScan source data, we will identify patients with a recorded diagnosis of non-valvular atrial fibrillation at risk for stroke who initiated anticoagulant medications between January 2009 and June 2012. Additional increments of data will be added as they become available (in 6 month intervals). Data from the time period before dabigatran was launched will be used to describe the characteristics of warfarin patients before the availability of NOAC, and to evaluate a potential shift in characteristics of warfarin patient over time as NOAC enter the market.

Inclusion criteria²:

- Any person within the source data who had a diagnosis of atrial fibrillation recorded (ICD-9 Dx code of 427.31, atrial fibrillation) and received a dispensing of an anticoagulant medication (warfarin and dabigatran for the initial analysis; with others to be added as they become available for stroke prevention in later time intervals) in the timeframe of the study.
- The first dispensing is preceded by at least 12 months continuous enrollment in the study database, defined as <32 days enrollment gap using enrollment and disenrollment dates. The study will thus focus on 'new initiators' defined operationally as no dispensing of any anticoagulant in the prior 12 months. Note that new initiators will turn into prevalent users over time.
- Patients' follow-up will end when there is a treatment gap of ≥ 30 days. If the same patient re-initiates treatment later on – after a treatment gap of ≥ 12 months –, (s)he may re-enter the cohort at that time (an indicator variable will be created to identify such patients, known as former users).
- 18 years or older at the time of treatment initiation
- CHA₂DS₂-VASc score³ ≥ 1

Exclusion criteria:

- patients with less than 12 months continuous enrollment in the study database without anticoagulant use before the first dispensing of anticoagulant medication.
- Patients with missing or ambiguous age or sex information.
- Patients with documented evidence of valvular disease defined as at least 1 inpatient or outpatient ICD-9 Dx code of [R11-4334]
 - 394.x (diseases of mitral valve)
 - 395.x (diseases of aortic valve)
 - 396.x (diseases of mitral and aortic valve)
 - 397.x (diseases of other endocardial structures)
 - 398.9x (other and unspecified rheumatic heart diseases)
 - V42.2 (heart valve replaced by transplant)
 - V43.3 (heart valve replaced by a mechanical device/prosthesis)
- OR

² A full description of all diagnostic and procedure codes included in this protocol is provided in [Appendix 3](#).

³ See [Table 7](#) in section 3.5 for CHA2DS2-VASc components and calculation

ICD-9 procedure code 35.1x (open heart valvuloplasty without replacement), 35.2x (replacement of heart valve) [R03-1232]

OR

one of the following CPT codes:

33660-33665 (atrioventricular valve repair)

33400-33403 (aortic valve valvuloplasty)

33405 (Replacement, aortic valve, with cardiopulmonary bypass; with prosthetic valve other than homograft or stentless valve)

33420-33430 (mitral valve repair/valvuloplasty/replacement)

33460 (valvectomy, tricuspid valve, with cardiopulmonary bypass)

33463-33468 (tricuspid valve repair/valvuloplasty/replacement)

33475 (replacement, pulmonary valve)

33496 (prosthetic valve dysfunction repair)

0257T (implantation of catheter-delivered prosthetic aortic heart valve; open thoracic approach)

0258T (transthoracic cardiac exposure for catheter-delivered aortic valve replacement; without cardiopulmonary bypass)

0259T (transthoracic cardiac exposure for catheter-delivered aortic valve replacement; with cardiopulmonary bypass)

0262T (implantation of catheter-delivered prosthetic pulmonary valve, endovascular approach)

[figure not shown]

Figure 1

Patient selection flow chart for initial cohort

3.2.1 Study size

This study will be estimating anticoagulant utilization parameters within a sampled population. The precision of these estimates will depend on the numbers of patients on which the estimate is made, and features of the estimate itself. The number of patients receiving anticoagulant medication and meeting study selection criteria is unknown at this stage. However, we assume that between 10,000 and 15,000 patients per year will meet selection criteria as having used warfarin or a newer anticoagulant so that by the end of the study (data from 2009-2015), there will be a total of at least 100,000 patients in each data source. (source: These are projections based on preliminary counts in the available UnitedHealth data)

The precision of proportion estimates (e.g. prevalence) is a function of the proportion and the number of patients contributing to the proportion (precision = standard error = $\sqrt{p(1-p)/n}$). As indicated in the table below, across a range of estimates provided, the precision for a prevalence estimate of 10% or 20% is less than 5% even for sample sizes that will likely be present in subgroups described in this study.

Table 1 Precision of estimates for proportion measures

Numerator	Denominator	Prevalence	95% CI	Precision (s.e.)
10	100	10%	4.9%-17.6%	3.0%
100	1,000	10%	8.2%-12.0%	0.9%
1,000	10,000	10%	9.4%-10.6%	0.3%
10,000	100,000	10%	9.8%-10.2%	0.1%
20	100	20%	12.7%-29.2%	4.0%
200	1,000	20%	17.6%-22.6%	1.3%
2,000	10,000	20%	19.2%-20.8%	0.4%
20,000	100,000	20%	19.8%-20.2%	0.1%

For continuous measures such as medication possession ratio ((MPR), see [Table 3](#)), the precision depends on the number of subjects on whom the estimate is made and the variability of the measures (precision = standard error = $\sqrt{\text{standard deviation}^2/n}$). As indicated in the table, the precision for a continuous measure is 5% or less even for measures that apply to strata that represent subgroups to be defined in this study.

Table 2

Precision of estimates for continuous measures

Sample Size	Mean	SD	Precision (s.e.)
100	1	0.5	5.0%
1,000	1	0.5	1.6%
10,000	1	0.5	0.5%
100,000	1	0.5	0.2%

By the end of the study, with a projected 100,000 patients meeting selection criteria, the various adherence measures will be estimated with a precision of 1% or less, except within fairly small strata.

3.3 EXPOSURES

- Initiation of oral anticoagulant medication (i.e., no use in the prior 12 months) represents the primary exposure.
- Utilization patterns will be defined by individual oral anticoagulant: warfarin and dabigatran for the initial cohort (Jan 2009-June 2012), as well as rivaroxaban and other NOACs as they enter the market within the study time horizon for subsequent cohorts (July 2012- Dec 2015).

3.4 OUTCOMES

Patterns of anticoagulant medication use will be identified on the basis of a pharmacy dispensing. Pharmacy dispensing is considered the most accurate utilization measure short of electronic pillcounting caps. [\[R13-0543\]](#)

The primary outcomes considered include the proportion of patients dispensed specific anticoagulants and anticoagulant doses (for NOAC), as well as a description of the characteristics of these patients.

In addition, a variety of measures will be derived from features of the dispensing data, including: number of dispensings, characteristics of dispensings (dose, and days supplied), along with persistence measures (e.g., proportion with a single dispensing, proportion remaining on therapy over time, time until treatment switch or discontinuation). [\[R13-0542; R12-3689; P06-11504\]](#)
Treatment persistence over time constitutes the secondary outcome,

Table 3

[figure not shown]
Definition of utilization measures

Measure	Definition
Days supplied*	Number of days supplied by a dispensing
Dose**	Presumed dose based on # tablets, mg per tablet, and number of days
One dispensing only	Number (and fraction) of first anticoagulant recipients with no second dispensing
Persistence	Fraction of anticoagulant users with continued dispensings. Patients will be classified as persistent if they possess medication at the specified time point. Grace period of 14 days will be allowed to obtain an additional refill.
Anticoagulant switch	Dispensing of another anticoagulant within <30 days of the end of days supplied of the previous medication
Anticoagulant discontinuation	Treatment gap of ≥ 30 days (i.e., no dispensing of anticoagulant medication within 30 days of the end of days supplied)

*: Days supply likely reflects use patterns in a commercial insurer such as United Health or MarketScan.

**: Estimation of dose will be challenging during the dose titration period for warfarin. We explore warfarin dose over time and assess the feasibility of estimating average dose, seeking to identify maintenance dose (i.e., dose needed for consistent therapeutic INR).

***:

Notes:

Incident user: Patient with no dispensing of an oral anticoagulant in the prior 12 months

(potential) prevalent user: Patients with <12 months enrollment before first observed dispensing. Since these patients could have been treated in the prior 12 months (treatment status during the unobserved time period is unknown), they are considered 'potential' prevalent patients.

Figure 2

Illustration of cohort entry and subsequent treatment patterns

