3.6.1 Main analyses

Analyses in this protocol are inherently descriptive in nature. The analyses described below will initially be conducted for the base cohort (Jan 2009- June 2012 data). Analyses will be updated at 6-month intervals as more data become available for the existing cohort(s) and new users are identified within the additional time period (July 2012- Dec 2015 data). As new data become available, we will characterize the patients newly initiated on treatment during that time period separately, in order to enable characterization of the shift in patient characteristics and use over time. In addition, short and long-term outcomes for the already existing cohorts (i.e., patients identified in previous time periods) will be updated with the newly available information in terms of switches, discontinuations, adherence and persistence.

A 12-month time window of no treatment is used to define a “new” treatment episode (i.e., incident user). Patients who re-initiate treatment after a treatment gap of \geq 12 months will re-enter the cohort as former users.

Primary outcomes:

Treatment initiation over time:

The yearly anticoagulation initiation rate will be estimated as the proportion of patients who initiated treatment among the source cohort of patients with non-valvular atrial fibrillation who met the study inclusion criteria and were not already on treatment. To identify the

source cohort of treatment candidates in a given calendar time window (i.e., the denominator for the rate), all patients with at least one day eligibility will be identified. A random date within the first eligibility period (if more than one) within the calendar time window will be selected and set as the index date. The cohort inclusion and exclusion criteria will be evaluated using this index date. Patients who were dispensed an anticoagulant before the assigned index date (prevalent users) will be removed from the denominator, unless they are identified as new initiators (i.e., included in the numerator) for that particular time period.

Characteristics of anticoagulant users:

The analyses will describe the proportion of patients treated with various oral anticoagulants, as well as the characteristics of these patients. For the NOACs, the starting dose will also be considered. Analyses will be conducted

as well for the combined cohort of incident and former users. Characteristics for the combined cohort will be presented in the core set of tables;

—
—
—

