Data prior to the launch of dabigatran in October 2010 will be used to characterize warfarin patients before the NOACs became available, and to evaluate the potential shift in patient characteristics over time. A comparison of patient characteristics across treatment groups will only be conducted within a common time window.

Secondary outcomes:

Utilization measures: Non-persistence

To ensure a valid comparison of utilization measures ([Table 3](#)), patients exposed to the various NOACs will be matched to warfarin on an exposure propensity score (PS) in a 1:1 fixed ratio using a nearest neighbor technique and a caliper of 0.05. In addition, the patients

will be matched within calendar quarters (3 month periods).

Briefly, all covariates listed in [REDACTED] will be included in a logistic regression propensity score (PS) model without further variable selection. In addition to demographic information, variables included in the PS were identified based on the a-priori expectation that they might be both associated with choice of anticoagulant and risk factors for study outcomes so that they represent likely confounding variables in a comparative safety and effectiveness analysis. The underlying assumption is that these variables capture the most important predictors of treatment persistence.

Balance of baseline characteristics in the matched cohorts will be evaluated. The utilization measures included in [Table 3](#) will be described for the PS-matched cohort. To properly account for differential follow-up, survival type analyses (i.e., Kaplan-Meier) will be used to describe time from treatment initiation to non-persistence (discontinuation or switch).

Number of patients at risk for this treatment outcome will be provided at 3-month intervals.

The various analyses are summarized below:

Analysis	Population	Outcome measure	Outcome type
Treatment initiation over time	Source population	Yearly initiation rate	Primary
Characteristics of anticoagulant users	Treatment cohort - Unmatched - Matched	Baseline characteristics	Primary
Utilization measures	Matched treatment cohort	- Treatment non-persistence (KM)	Secondary

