11. APPENDICES

11.1 APPENDIX 1: LIST OF FIGURES AND TABLES

List of Core Tables

These tables will be generated separately for United and MarketScan; and will be presented only for incident and former users combined, unless meaningful differences between characteristics of incident and former users are observed.

- | | |
|----------|--|
| Table 1 | Treatment initiation over time |
| Table 2 | Characteristics of Anticoagulation Users: all time periods combined |
| Table 3 | Characteristics of Anticoagulation users: latest time period |
| Table 4 | Adherence metrics for Anticoagulation users: all time periods combined |
| Table 5 | Adherence metrics for Anticoagulation users: latest time period |
| Table 6 | |
| Table 7 | Characteristics of continuers, switchers (combined and by treatment switched to), and discontinuers at 3 months : characteristics measured during the 12-months preceding treatment initiation . |
| Table 8 | Characteristics of continuers, switchers, and discontinuers at 3 months: characteristics measured during the 3-months immediately preceding the event (day of switch, day of discontinuation, day 90 for continuers). |
| Table 9 | Characteristics of continuers, switchers, and discontinuers at 6 months : characteristics measured during the 12-months preceding treatment initiation . |
| Table 10 | Characteristics of continuers, switchers, and discontinuers at 6 months: characteristics measured during the 3-months immediately preceding the event (day of switch, day of discontinuation, day 180 for continuers). |
| Table 11 | Characteristics of continuers, switchers, and discontinuers at 12 months : characteristics measured during the 12-months preceding treatment initiation . |
| Table 12 | Characteristics of continuers, switchers, and discontinuers at 12 months: characteristics measured during the 3-months immediately preceding the event (day of switch, day of discontinuation, day 360 for continuers). |

List of Core Figures

[figure not shown]
These figures will be generated separately for United and MarketScan

- Figure 1: Cumulative incidence of treatment switches - 30 day gap

Figure 2: Cumulative incidence of treatment discontinuation – 30 day gap

Figure 3: Cumulative incidence of treatment switches or discontinuation – 30 day gap

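### Table 3 defines the single-dispensing fraction without a time horizon or censoring rule in the readable text, so patients whose data end before a refill is due count as single-fill patients

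*Combined protocol and SAP*

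**What the plan says.** Section 3.4 lists persistence measures, among them "proportion with a single dispensing, proportion remaining on therapy over time, time until treatment switch or discontinuation". Table 3 defines the first of these as "Number (and fraction) of first anticoagulant recipients with no second dispensing". Two neighbouring rows of Table 3 do carry a time rule: discontinuation needs 30 days without a dispensing after the end of supply, and persistence is read at a specified time point with a 14-day grace period.

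Section 3.6.1 says that the Table 3 measures will be described in the propensity-score matched cohort, with matching inside calendar quarters. On unequal follow-up it says: "To properly account for differential follow-up, survival type analyses (i.e., Kaplan-Meier) will be used to describe time from treatment initiation to non-persistence". No other utilization measure is given a censoring method there.

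The analyses are repeated every six months. For each new block, Section 3.6.1 says "we will characterize the patients newly initiated on treatment during that time period separately". Appendix 1 lists Core Table 4 (adherence metrics, all periods combined) and Core Table 5, titled "Adherence metrics for Anticoagulation users: latest time period".

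**The concern.** A second dispensing cannot be seen if the data stop first. A patient who starts within one days' supply of the data cut, or who disenrols in that time, enters the numerator whatever they go on to do. The reported fraction therefore mixes early abandonment with truncation.

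The truncated part grows with days' supply and shrinks as the window of starts lengthens. The figure can therefore differ between drugs with different fill lengths, between NOACs launched at different dates, and between successive reports on one drug, with identical patient behaviour. A reader would take the single-fill fraction as a measure of early abandonment. Section 3.2.1 expects adherence measures to be estimated to within 1% or less by the end of the study, but more patients do not reduce this error.

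**Working it through.** **The plan's own figures.** The documents give no value for the single-dispensing fraction. The nearest figure is Table 1, the precision of a proportion, s.e. = √(p(1−p)/n). For 10/100 this is √(0.1×0.9/100) = 3.0%, and for 20/100 it is √(0.2×0.8/100) = 4.0%. All eight rows reproduce to rounding, and the intervals are exact binomial ones. Table 1 covers sampling error only.

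**Inputs from the documents.** Six-month blocks (July-December = 184 days); dabigatran launched October 2010 and base cut June 2012 (639 days); whole study 2009-2015 (2,556 days); 10,000 to 15,000 patients a year (Section 3.2.1); 30-day gap (Table 3); illustrative proportions of 10% and 20% (Table 1).

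**Assumptions, not in the documents.** Starts are uniform over a window of W days ending at the data cut. Every first fill has S = 30 or S = 90 days. Refill falls exactly at day S. Nobody disenrols.

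**Formula.** The share with no time to refill is S/W. If the true fraction is p, the raw fraction is p + (1−p)·S/W.

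| Window of starts | W | S/W (30-day; 90-day) | Raw if p = 10% | Raw if p = 20% |
|---|---|---|---|---|
| Latest 6-month block | 184 | 16.3%; 48.9% | 24.7%; 54.0% | 33.0%; 59.1% |
| Drug on the market 12 months | 365 | 8.2%; 24.7% | 17.4%; 32.2% | 26.6%; 39.7% |
| Dabigatran, base cut | 639 | 4.7%; 14.1% | 14.2%; 22.7% | 23.8%; 31.3% |
| All of 2009-2015 | 2,556 | 1.2%; 3.5% | 11.1%; 13.2% | 20.9%; 22.8% |

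Example: 0.10 + 0.90 × 30/184 = 0.247. The bias is 13 to 44 points in a 6-month block and 1 to 3 points over the whole study.

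**Refill delay.** A simulation with a 182-day block and refills from 5 days before to 29 days after the end of supply gave raw fractions of 30.8% (30-day) and 60.5% (90-day) for a true 10%. Refilling exactly on time is thus the milder assumption.

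**Days' supply after matching.** Two drugs with the same start dates (W = 184) and p = 10% differ by 0.90 × 0.10 × (90−30)/184 = 2.9 points for every 10-point difference in their share of 90-day first fills. Calendar matching does not touch this.

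**MarketScan.** By the Section 8 milestones its last increment runs April-December 2015, or 275 days. The truncated shares there are 30/275 = 11% and 90/275 = 33%.

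**Check of the remedies.** In the same simulation, with windows of 182 to 2,556 days, two estimates were read at S + 30 days: Kaplan-Meier for time to second dispensing, and the fraction with no second dispensing by that day among patients observed at least that long. Both returned 9.9%-10.1% for a true 10% and 19.9%-20.1% for a true 20%.

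**Cost of the restriction in a 184-day block.** Kept: 1 − 60/184 = 67% (30-day) or 1 − 120/184 = 35% (90-day). Of 5,000 to 7,500 starters, all drugs together, that is about 3,370 to 5,054 or 1,739 to 2,609. The standard errors are 0.4-0.7 and 0.6-1.0 points for proportions of 10% to 20%.

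**The case against.** The best case for the plan has five parts.

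- **Removed text.** Section 3.2.1 points to Table 3 for the medication possession ratio, but no such row is readable, and one footnote is blank. A follow-up rule could sit there. This stands as a caveat: the point can be made only about the readable definition.
- **Placement.** A reader might infer that Core Table 5 will certainly carry this fraction and so show the largest bias. The documents do not say so. Section 3.4 calls it a persistence measure, Section 3.6.1 names adherence and persistence separately, and Section 8 lists adherence apart from the utilization measures. Table 3 measures are assigned to the matched cohort, while the titles of Core Tables 4 and 5 speak of users in general. The latest-block figures are therefore conditional.
- **Size.** A reader might take 54% as the expected error. It needs every first fill to be 90 days. Over the full study the bias is 1 to 3 points, and existing cohorts are updated at each cut, so truncation in earlier blocks resolves.
- **Between-drug contrast.** A reader might infer a distorted NOAC-versus-warfarin comparison. Matching within calendar quarter gives both arms similar time to the cut, and Section 8 says the tables make no explicit comparisons. What remains is the days'-supply part, side-by-side NOACs with different launch dates, and change between reports.
- **Redundancy.** Early abandonment is already estimated with censoring by the Kaplan-Meier analysis and shown in the cumulative-incidence figures. That is true, and those results are not in question. The single-fill fraction is nevertheless a named measure that Section 3.6.1 says will be described, and a definition that counts truncated patients as single-fill patients should not stand beside the censored analysis.

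**Conclusion.** The point holds in a limited form. As readable, the definition overstates the single-fill fraction, always upwards, and the plan's stated handling of differential follow-up does not reach it. For a true 10%, the raw value would be about 11% to 13% over 2009-2015, 14% to 23% for dabigatran in the base cut, and 25% to 54% if reported for a 6-month latest block. The lower end assumes all 30-day first fills and the upper end all 90-day fills, with uniform starts and refill at the end of supply. Refill delay raises these values. Disenrolment before a refill acts in the same direction and was not modelled. The true fraction and the mix of fill lengths are not in the documents.

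The documents do not support saying that the main persistence result is biased, that the matched NOAC-warfarin contrast is seriously distorted, or that Core Table 5 is known to contain the error. The change is still worth making: the measure is reported repeatedly, the bias can far exceed the stated precision in recent data, and the correction is small.

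**What to change.** Redefine the Table 3 row as the Kaplan-Meier probability of no second dispensing by the first dispensing's days' supply plus 30 days (the plan's own gap), censoring at disenrolment or data cut. Because that day depends on the fill, estimate it within strata of drug and first days' supply, and combine strata weighted by number of starters. Where no patient in a stratum has been observed that long, report it as not yet estimable.

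A simpler option is the fraction with no second dispensing by that same day among initiators observed at least that long, with the number excluded. Both parts are needed: restricting the denominator alone leaves the numerator without a horizon.

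State which core tables carry the measure, and use the same definition in each.

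The cost is a changed row and a little programming. Kaplan-Meier discards nobody. Under the simpler option, about one third (30-day) to two thirds (90-day) of latest-block starters drop out of this one measure until the next update. The loss is larger for longer fills, so it should be shown by days' supply.
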